6.3 Other Study Related Definitions

Analytical Window Assignments

Analytical windows will be used to summarize protocol specified parameters according to the protocol schedule. This algorithm is provided in [Appendix A](#).

Analytical Window Assignments

Analytical windows will be used to summarize protocol specified parameters according to the protocol schedule.

Exposure to Investigational Product

For each subject who received at least one dose of IP, the number of days of IP exposure Period is calculated as [(Date of Last Dose of Investigational Product Received – first dose date + 1) + 28 days]. The exposure to IP in study month = exposure to IP / 28 days.

Study Exposure

For each randomized subject, study exposure is defined as time from the randomization date to the end of study date.

Evaluation Periods for Different Analysis Approaches

The evaluation period of the on-treatment approach begins from the date of randomization, and subjects will be censored at the last dose of investigational product plus 3 months or end of study, whichever is earlier.

The evaluation period of the on-study approach begins at the date of randomization and subjects will be censored at the end of study date.

Treatment Emergent Adverse Events

Treatment emergent adverse events are adverse events occurring on or after the first dose of IP.

Adverse Events of Special Interest

Adverse events falling into categories of special interest (EOI) will be reported according to the special interest category. The categories of interest for the study are:

- Hypertension
- Ischemic Heart Disease
- Cardiac Failure
- Cerebrovascular Disorders
- Dialysis Vascular Access Thrombosis
- Embolic and Thrombotic Events (including arterial thromboembolic events, venous thromboembolic events and vessel type unspecified and mixed arterial and venous)
- Convulsions
- Antibody-Mediated Pure Red Cell Aplasia (PRCA)
- Hypersensitivity
- Lack of Efficacy-Effect
- Malignancies

The definition of each EOI may be modified and a new EOI may be added based on findings from ongoing pharmacovigilance. Updates of the search strategy due to MedDRA upgrades or other reasons may not trigger a SAP amendment. However, the most recent EOIs per Amgen EOI search strategy will be used at the time of the analysis and these search terms will be included in an appendix of the study report.

Adverse Event Subject Incidence

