Hb variability

At any study visit, the Hb variability is the intra-subject Hb standard deviation over the prior 6 months. The Hb variability will be calculated at each scheduled visit from Week 25.

Initial Hb Response

Initial Hb response is defined as the change of Hb concentration from baseline at Week 5.

Initial Hb Response Subgroup

Initial Hb response subgroups are defined as the initial Hb response quartiles based on the initial Hb response analysis set subjects ([Section 7.3](#)) from both treatment groups.

Dose

The dose referred in this analysis plan is the darbepoetin alfa dose from the IP administration. The dose from a placebo injection equals zero darbepoetin alfa dose.

Weight-based Dose at Specific Study Visit

The weight-based dose at any time point = Dose in μg at specific study visit / subject's screening weight in kg.

Cumulative Dose at Specific Study Visit

The cumulative dose at specific study visit = sum of all darbepoetin alfa doses received from Study Day 1 through the specific study visit.

Average Cumulative Dose per 4 Week at Specific Study Visit

Average cumulative dose per 4 week at specific study visit is defined as the 4-week equivalent cumulative dose received at specific study visit.

Average Cumulative Weight-adjusted Dose per 4 Week at Specific Study Visit

Average cumulative weight-adjusted dose per 4 week at specific study visit = average cumulative dose per 4 week at specific study visit / the screening weight in kg.

Transfusion Subgroups

Subjects will be categorized into transfusion subgroups based on the number of transfusion events: No transfusion event, one transfusion event, more than 1 transfusion event.

Transfusion subgroup (on-treatment approach) will be defined using the number of transfusion events where the start date of the transfusion event falls within the evaluation period of the on-treatment approach.

Transfusion subgroup (on-study approach) will be defined using the number of transfusion events where the start date of the transfusion event falls within the evaluation period of the on-study approach.

Time to Event Derivation

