For time to event such as time to first transfusion, or time to first major clinical event (eg, major adverse cardiovascular events (MACE), all-cause mortality), time to event is derived from the randomization date to the date of specific event. Subjects that do not experience the event will be censored. For time to event analysis using the on-treatment approach, the censoring date is the last dose date + 3 months (84 days) or the end of study date, whichever is earlier. For time to event analysis using the on-study approach, the censoring date is the end of study date.

Context surrounding RBC Transfusion

Clinical context surrounding RBC transfusion will be collected for each RBC transfusion event, and will be reviewed by an independent Clinical Endpoint Committee (CEC). The clinical context includes the primary reason for the transfusion event, the transfusion setting (eg, dialysis center, intensive care unit, emergency department), Hb at the time of the first transfusion of the transfusion event, clinical events (eg, bleeding, surgery), symptoms and vital signs of concerns.

Total number of units of RBC transfused

The total number of units of RBC transfused using the on-treatment approach is the sum of RBC units transfused between the randomization date and the earlier date of the last dose date + 3 months (84 days) and the end of study date. The total number of units of RBC transfused using the on-study approach is the sum of RBC units transfused between the randomization date and the end of study date.

Number of Days Hospitalized

This is the total number of days of hospitalization between the randomization date and earlier of the date of last IP + 3 months (84 days) and the end of study date for the on-treatment approach; between the randomization date and the end of study date for the on-study approach. Duration of each hospitalization stay is calculated as day of discharge - day of admission + 1. Hospitalizations with identical admission and discharge days will be counted as a hospitalization with duration of 1 day.

Area under the Curve (AUC) Calculation

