10.5.1 Analyses of Primary Efficacy Endpoint(s)

The primary analysis of the primary endpoint will be conducted using the full analysis set. The evaluation period will begin from the date of randomization, and subjects will be censored at the last dose of investigational product plus 3 months or end of study, whichever is earlier (on-treatment approach). For the primary endpoint, the proportion of subjects in each treatment group receiving at least 1 RBC transfusion during the evaluation period will be presented with 2-sided 95% CIs. The difference in proportions between treatment groups will be described with 2-sided 95% CIs. Confidence intervals

will be derived using normal approximation. The relative risk ratio and its 95% CI will be described using the Cochran-Mantel-Haenszel statistic controlling for the stratification factors.

The primary analysis will be repeated by subgroups of stratification factors used at randomization, and also by subgroups of age, gender, race, baseline Hb concentrations, baseline eGFR and diabetes at baseline.

Sensitivity analyses of the primary endpoint will be repeated using:

- All randomized subjects with the evaluation period beginning at the date of randomization and subjects will be censored at the end of study date (on-study approach).
- Completer analysis set with the evaluation period between the date of randomization and the end of study date

Sensitivity analyses will be performed to assess the impact of potential differential follow up on the primary endpoint. Exposure-adjusted subject incidence of receiving at least 1 RBC transfusion will be calculated with 95% CI using Chi-square approximation to the Poisson distribution for both on-treatment and on-study approaches.

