10.5.2 Analyses of Secondary Efficacy Endpoint(s)

Total number of units of RBC transfused per subject will be described for each treatment group, and will be analyzed using a negative binomial regression model which will

include the stratification factors used at randomization. As a sensitivity analysis, exposure adjusted event incidence of total number of units RBC transfused will be presented with 95% CI using Chi-square approximation to the Poisson distribution. These analyses will be performed using both on-treatment approach with the full analysis set and on-study approach with all randomized subjects.

Time to first RBC transfusion will be analyzed using both on-treatment approach with the full analysis set and on-study approach with all randomized subjects. It will be analyzed by each treatment group with Kaplan-Meier curves, Kaplan-Meier percentiles and estimates at 6, 12, 18, and 24 months, the number of subjects censored, and the number of subjects transfused. A supportive analysis will be performed using Cox proportional hazards model (Cox, 1972) stratified by the stratification factors used at randomization to evaluate the difference between the treatment groups. The hazard ratio and its corresponding 95% CI will be estimated.

Average achieved Hb concentration while receiving investigational product will be described as average Hb using the area under the curve (AUC) method. The median of the difference in achieved Hb concentration (Hodges–Lehmann estimate) between treatment groups will be calculated and 2-sided 95% confidence limits will be derived by using a nonparametric Wilcoxon rank-sum statistic (Hollander and Wolfe, 1973). As a sensitivity analysis, the above analyses will be repeated excluding Hb concentrations measured within 3 months (84 days) from an RBC transfusion.

Cumulative doses of darbepoetin alfa adjusted for investigation product exposure time (eg, average cumulative darbepoetin alfa dose per 4 week) will also be summarized, and the median of the difference (Hodges–Lehmann estimate) between treatment groups will be calculated and 2-sided 95% confidence limits will be derived by using a nonparametric Wilcoxon rank-sum statistic.

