11. CHANGES FROM PROTOCOL-SPECIFIED ANALYSES

There are no changes to the protocol-specified analyses.

12. LIST OF PLANNED TABLES, FIGURES AND LISTINGS [TFLs]

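### The Poisson 95% CI for the exposure-adjusted rate of RBC units ignores clustering of units within subjects and is too narrow once transfused subjects average more than about 1.33 units

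*SAP*

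**What the plan says.** SAP 10.5.2 describes total units per subject and analyses them with a negative binomial regression that includes the stratification factors. The text for the sensitivity check reads: "exposure adjusted event incidence of total number of units RBC transfused will be presented with 95% CI using Chi-square approximation to the Poisson distribution". Protocol 10.5.2.2 specifies the same method, so the two documents agree. Both apply it to the on-treatment and on-study approaches, and SAP 12.1 lists a table for each.

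The quantity counted is units. SAP 6.3 gives the on-treatment total as "the sum of RBC units transfused between the randomization date and the earlier date of the last dose date + 3 months (84 days"; counting stops sooner if the subject leaves the study before then. A matching on-study total is also defined. SAP 6.3 also shows that one subject can contribute many units. Its transfusion subgroups are "No transfusion event, one transfusion event, more than 1 transfusion event", and the clinical context to be collected includes "Hb at the time of the first transfusion of the transfusion event", so a single event can hold several transfusions.

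SAP 10.5.1 uses the same kind of interval for a different quantity: "Exposure-adjusted subject incidence of receiving at least 1 RBC transfusion will be calculated with 95% CI using Chi-square approximation to the Poisson distribution". There each subject counts at most once.

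**The concern.** A chi-square (exact Poisson) interval for a total count is valid when the variance of the total equals its mean. Units do not arrive one by one and independently across the arm. Most subjects are expected to have none, and those who are transfused may receive several units at one event and may have further events. The plan recognises this by choosing a negative binomial model for the same count, then sets it aside in the sensitivity interval.

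At stake is the stated precision of each arm's unit rate. Transfusion burden is a secondary objective, and Protocol 2.3 lists total units among the considerations for a preferred regimen. In a trial built on estimation, readers judge evidence by interval width. An interval that is narrow only because it ignores clustering could be read as confirming the main analysis more firmly than it does.

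**Working it through.** **Inputs from the plan (SAP 3.2, Protocol 10.2).** Share transfused p = 0.25; n = 375 per group; 2-sided 95% intervals. The plan's own sizing reproduces: 2 × 1.96 × √(0.25 × 0.75/300) = 9.80%, within the 10% target, and 300/(1 − 0.20) = 375. The documents state no figure for the unit rate or its variance.

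**Assumed.** The distribution of U, the units per transfused subject. The documents do not give it, so a range is shown.

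**Step 1: variance against Poisson.** For units per subject Y, the mean is p·E[U] and the variance is p·E[U²] − p²·E[U]². Hence

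variance/mean = E[U²]/E[U] − p·E[U] ≥ (1 − p)·E[U],

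with equality when every transfused subject receives the same number. A Poisson interval needs this ratio to be 1.

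- At p = 0.25 the floor is 0.75 × E[U]: 0.75 at 1 unit, 1.5 at 2, 2.25 at 3, 3.0 at 4.
- The floor reaches 1 at E[U] = 1/(1 − 0.25) = 1.33. With spread between subjects, the ratio reaches 1 sooner.
- The result is not special to 25%. At 2 units the floor is 2(1 − p): 1.8 if 10% are transfused and 1.2 if 40% are.
- For comparison, a true Poisson process with 25% of subjects transfused implies only −ln(0.75)/0.25 = 1.15 units per transfused subject.

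**Step 2: coverage.** The normal approximation is 2Φ(1.96/√ratio) − 1. Simulation used 20,000 arms of 375 with chi-square limits and equal follow-up. The robust interval is log rate ± 1.96 × √Σ(y − rate × t)² / Σy, summed over subjects.

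| Units per transfused subject (assumed) | Variance/mean | Poisson coverage, approx. | Poisson coverage, simulated | Robust coverage | Width, robust/Poisson |
|---|---|---|---|---|---|
| exactly 1 | 0.75 | 98% | 98% | 95% | 0.85 |
| mean 1.5 (mix of 1 and 2) | 1.29 | 92% | 92% | 95% | 1.12 |
| exactly 2 | 1.50 | 89% | 89% | 95% | 1.21 |
| exactly 3 | 2.25 | 81% | 83% | 95% | 1.48 |
| mean 2.5 (2-unit events, geometric number) | 2.375 | 80% | 80% | 95% | 1.52 |
| mean 3 (same) | 3.25 | 72% | 72% | 95% | 1.78 |
| mean 4 (same) | 5.0 | 62% | 62% | 95% | 2.21 |

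**Step 3: other assumptions.** A separate simulation had 20% of subjects leaving at a uniform time and three shapes for U. Poisson coverage was 89.5%, 84.0% and 79.1% at a mean of 2 units (constant, 1 + Poisson, geometric); 81%, 76% and 66% at 3; and 74%, 69% and 59% at 4. The subject-level robust interval covered 94% to 95% throughout.

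**Step 4: one worked arm.** Suppose 94 of 375 subjects receive exactly 2 units each, 188 in all. The Poisson interval is 162.1 to 216.9 units, width 54.8. The subject-level standard error is √(375 × 0.75) = 16.77, where 0.75 = 0.25 × 0.75 × 2² is the variance per subject. That gives 188 ± 1.96 × 16.77 = 155.1 to 220.9, width 65.7, or 65.7/54.8 = 1.20 times as wide. This is the mildest case at 2 units, because it has no spread between subjects.

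**The case against.** The strongest reply is that the defect depends on a number the documents do not give. At 1 unit per transfused subject the planned interval is conservative, and at a mean of 1.25 it is close to nominal. The reporting category for repeat events shows that they are possible, not how common they will be. This stands as a limit on what can be claimed. It does not rescue the method, because the subject-level interval holds its coverage across the whole range and is narrower at 1 unit. The sponsor need not know the mean to prefer it.

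Second, overdispersion is already handled in the main negative binomial analysis, and a sensitivity analysis may use a different distribution. The first part stands and is why the impact is modest. But this rate is the only unit analysis that the readable text describes as exposure-adjusted, and replacing a model that allows overdispersion with an interval that assumes none does not test robustness.

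Third, nothing is decided on this interval: no hypothesis is tested, no between-arm contrast of this rate is planned, and the descriptive summary sits beside it. This also stands and limits the consequence.

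A reader might also infer that the on-treatment rate has mismatched numerator and denominator, because exposure to investigational product ends at the last dose plus 28 days ("first dose date + 1) + 28 days") while units are counted for up to 84 days. The documents do not support that. SAP 6.3 defines an on-treatment evaluation period, units are counted over that same window, and SAP 12.1 tabulates the rate by the on-treatment approach. Nothing ties this rate to the product-exposure definition. The code appendix is also redacted, so silence in the text cannot be read as an omission.

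**Conclusion.** The concern holds, conditionally. The planned interval assumes independent units, and at the plan's 25% transfused it is too narrow whenever transfused subjects average more than about 1.33 units, whatever the distribution. Coverage is 98% at exactly 1 unit, about 89% at exactly 2 and 83% at exactly 3. The 62% at a mean of 4 also rests on an assumed geometric number of 2-unit events.

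Two stronger readings should be resisted. A reader might infer that this trial's interval will certainly fall far short of 95%; without the mean number of units, the documents cannot show that. A reader might also extend the criticism to the Poisson interval for subject incidence in SAP 10.5.1; it does not apply there, since each subject contributes at most one event. The unit-rate point estimate and the negative binomial analysis are likewise unaffected. What remains is overstated precision of a per-arm rate in a sensitivity analysis of a secondary endpoint: worth correcting, with modest consequences.

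**What to change.** In SAP 10.5.2, for the exposure-adjusted unit rate only, replace the Poisson interval with a subject-level robust (sandwich, log-scale) 95% CI or a subject-level bootstrap 95% CI. Keep the Poisson interval for subject incidence in SAP 10.5.1.

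Protocol 10.5.2.2 specifies the same Poisson method, so the change needs either a protocol amendment there or an entry in SAP section 11, which now states "There are no changes to the protocol-specified analyses".

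The cost is one change of wording, one record of the change and a few lines of code. No new data are needed, and the planned table rows in SAP 12.1 name no interval method, so they can stand. The downside is a wider interval, about 1.2 to 2.2 times at means of 2 to 4 units, which reflects the uncertainty actually present. If transfused subjects turn out to receive 1 unit each, the interval is narrower (0.85 times).

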4.1 Inclusion Criteria

- 4.1.1 Age 18 or older
- 4.1.2 Clinical history of advanced CKD not on dialysis with at least 1 historic estimated glomerular filtration rate (eGFR) < 45.0 mL/min/1.73m² at least 12 weeks prior to screening
- 4.1.3 **Not currently receiving dialysis with an** eGFR < 45.0 mL/min/1.73m², per the central laboratory during screening
- 4.1.4 Chronic anemia due to renal failure
- 4.1.5 Two Hb concentrations < 10.0 g/dL, at least 2 weeks apart during screening using the **modified** Hb point of care (POC) device

- 4.1.6 Iron replete, defined as a transferrin saturation (TSAT) \geq 20% and a ferritin \geq 100 ng/mL, per the central laboratory during screening
- 4.1.7 Vitamin B12 and folate replete, defined as a vitamin B12 level $>$ 180 pg/mL and a folate concentration $>$ 7 nmol/L, per the central laboratory during screening
- 4.1.8 Clinically stable in the opinion of the investigator
- 4.1.9 Subject has provided written informed consent

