10.1.3 Subgroups and Covariates

Subgroups and covariates to be considered include the stratification factors used at randomization, and the following baseline factors: age, sex, race, baseline Hb concentration and baseline eGFR. Subgroups are defined as

- Age: < 65, ≥ 65 and < 75, ≥ 75 years
- Gender: Female, Male
- Race: White, Black, Other
- Baseline Hb concentrations: <9.0, 9.0 – < 9.5, 9.5 – < 10.0 g/dL
- Baseline eGFR: < 30.0, ≥ 30.0 mL/min/1.73m²

Additional analyses may be performed if other prognostic factors emerge in this study or in this population.

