6.2 Demographics and Baseline Related Definitions

Age

Age will be calculated as the subject's (floor) integer age in years at the randomization date.

Screening Weight

Weight measured at the first screening visit, which the starting dose is calculated upon.

Baseline Hb Value

The baseline Hb value is defined as the mean of the 2 most recent non-missing Hb concentrations measured through the Hemocue device prior to or on the randomization date. If for any reason only 1 value is available, then that value will be used as baseline.

Baseline Values (other than Hb)

The baseline value is the last non-missing value measured prior to or on the randomization date.

Baseline Body Mass Index

The baseline body mass index (BMI) is calculated as [baseline weight (kg) / baseline height (m)²].

Change from Baseline

The arithmetic difference between a post-baseline value and baseline value for a given time point:

$$\text{Change from baseline} = (\text{post-baseline value} - \text{baseline value})$$

Percent Change from Baseline

The percent change from baseline for a given variable at a given time point is defined as:

$$100 \times [(\text{value at given time point} - \text{baseline value}) / \text{baseline value}]$$

Estimated Glomerular Filtration Rate

Estimated glomerular filtration rate (eGFR, mL/min/1.73m²) will be calculated using Chronic Kidney Disease Epidemiology Collaboration (CKD-EPI) equation

(Levey et al, 2009):

$$\text{eGFR} = 141 \times \min(\text{Scr}/\kappa, 1)^\alpha \times \max(\text{Scr}/\kappa, 1)^{-1.209} \times 0.993^{\text{Age}} \times 1.018 \text{ [if female]} \times 1.159 \text{ [if black]}$$

Where Scr is serum creatinine (mg/dL), κ is 0.7 for females and 0.9 for males, age is the age at the time the measurement is taken, α is -0.329 for females and -0.411 for males, min indicates the minimum of Scr/ κ or 1, and max indicates the maximum of Scr/ κ or 1.

Stratification Factors

- RBC transfusion received within 12 months prior to randomization: Yes, No
- Site practice setting: Nephrology, Non-nephrology, pre-specified by the specialty of the principal investigator at the time of site initiation

Baseline Subgroups

- Age: < 65, ≥ 65 and < 75, ≥ 75 years
- Gender: Female, Male
- Race: White, Black, Other
- Baseline Hb concentrations: < 9.0, ≥ 9.0 – < 9.5, ≥ 9.5 – < 10.0 g/dL
- Baseline eGFR: < 30.0, ≥ 30.0 mL/min/1.73m²
- Diabetes at baseline: Yes, No

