10. STATISTICAL METHODS OF ANALYSIS

10.1 General Principles

Descriptive statistics will be presented for all endpoints by treatment group. For continuous variables, these include number of observations, mean, standard error (SE) and/or standard deviation (SD), median, 25th percentile (Q1), 75th percentile (Q3), minimum and maximum. For categorical variables, the frequency and percentage are presented. For time to event endpoints: Kaplan-Meier curves, Kaplan-Meier percentiles, the number of subjects censored, and the number of subjects with events will be summarized. Confidence intervals will be constructed as 2-sided at the 95% level. Summaries of laboratory data, Hb and dose related parameters, and vital signs will be completed using the full analysis set, limited to measurements obtained while the subject is receiving the investigational product.

For variables that are summarized over time, the actual visit for a subject may not exactly coincide with their targeted scheduling. The visit windows defined in [Appendix A](#) will be used to assign evaluations to a most appropriate nominal visit for analysis and summarization.

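### The overall comparison of achieved Hb is not adjusted for baseline Hb or the randomisation factors, which leaves a probably small precision gain unused

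*SAP*

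**What the plan says.** For average achieved Hb, SAP 10.5.2 plans a Hodges–Lehmann estimate between the arms: "The median of the difference in achieved Hb concentration". For the interval, "2-sided 95% confidence limits will be derived by using a nonparametric Wilcoxon rank-sum statistic". Protocol 10.5.2.2 plans the same method. No covariate appears in either place.

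Protocol 10.1.3 reads: "Subgroups and covariates to be considered include the stratification factors used at randomization, and the following baseline factors: age, sex, race, baseline Hb concentration"; it then adds baseline eGFR. SAP 6.2 defines the covariate: "The baseline Hb value is defined as the mean of the 2 most recent non-missing Hb concentrations". Two readings below 10.0 g/dL are an entry condition (Protocol 4.1), taken "at least 2 weeks apart during screening using the" modified point-of-care device. The SAP still provides for a gap: "If for any reason only 1 value is available, then that value will be used as baseline".

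Baseline Hb does appear elsewhere in the Hb analyses. SAP 10.5.2 repeats the achieved-Hb summary by baseline-Hb subgroup. The table list in SAP 12.1 repeats the full analysis, Hodges–Lehmann estimate included, by the same subgroups. SAP 10.5.3 summarises change from baseline at each visit. The randomisation factors are used in the Mantel–Haenszel relative risk, the Cox models and the negative binomial model (SAP 10.5.1 and 10.5.2), but not in the overall achieved-Hb estimate.

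**The concern.** The trial tests no hypothesis (SAP 5), so for each comparison the estimate and its interval are the result. Describing the difference in achieved Hb is a stated secondary objective. A baseline measurement that predicts the outcome can remove part of the outcome's variance and part of the chance imbalance between arms. The plan holds such a measurement, names it as a possible covariate, and leaves it out of the overall estimate. What is at stake is the width of one secondary interval.

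A related gap concerns timing. Protocol 2.3 says the fixed dose was chosen by simulation to give about the same mean Hb as titration at the end of the study. The achieved-Hb endpoint averages from Week 13 to the last dose (SAP 6.3), which is a different quantity. Hb by visit is only summarised by arm, "limited to measurements obtained while the subject is receiving the investigational product". No planned analysis gives the arm difference at the end of treatment with an interval.

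**Working it through.** **The plan's own figures.** The SAP gives no SD, correlation or interval width for achieved Hb. Its only precision figures concern the primary endpoint (SAP 3.2), and they reproduce with p = 0.25:

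- One arm, half-width 0.05: 1.96² × 0.25 × 0.75 / 0.05² = 288.1, so 289.
- Difference, half-width 0.07: 2 × 1.96² × 0.25 × 0.75 / 0.07² = 294 per arm.
- The stated 300 per arm covers both, and 300 / 0.8 = 375.

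The 300 per arm is carried forward below.

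**Gain from adjustment.** Let r be the correlation of baseline with achieved Hb (assumed). With a common slope, the interval is multiplied by √(1 − r²), and the equivalent sample size is 300 / (1 − r²). The unadjusted half-width at 300 per arm is 1.96 × √(2/300) = 0.160 SD.

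| r (assumed) | Narrower by | Adjusted half-width (SD) | Equivalent n per arm |
|---|---|---|---|
| 0.1 | 0.5% | 0.159 | 303 |
| 0.2 | 2.0% | 0.157 | 312 |
| 0.3 | 4.6% | 0.153 | 330 |
| 0.4 | 8.3% | 0.147 | 357 |
| 0.5 | 13.4% | 0.139 | 400 |

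**Why the low end is likelier.** Entry below 10.0 g/dL restricts the range of baseline Hb. If the baseline SD is cut to a fraction u, then r becomes r·u / √(1 − r² + r²u²). An unrestricted r of 0.5 falls to 0.225 at u = 0.4 and 0.419 at u = 0.8 (u assumed), a gain of about 3% to 9%. Titration on current Hb and the start of the outcome at Week 13 weaken the link further.

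**Does the formula carry over to a rank-based interval?** A simulation (300 per arm, 300 runs per setting) compared mean 95% interval widths with the planned Hodges–Lehmann interval:

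| r, residuals | Hodges–Lehmann on adjusted values | ANCOVA |
|---|---|---|
| 0, normal | −0.1% | −2.4% |
| 0.3, normal | −4.7% | −7.0% |
| 0.5, normal | −13.5% | −15.5% |
| 0, t(3) | 0.0% | +31.2% |
| 0.3, t(3) | −11.0% | +20.8% |
| 0.5, t(3) | −25.8% | +0.4% |

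With unequal slopes (r = 0.5 in the fixed-dose arm, 0.1 in the titrated arm, normal residuals) the rank-based gain was 4.7%. With r = 0.3 and 0 it was 1.2%. The rank-based version was not wider than the planned interval in any setting tried; ANCOVA was wider under most of the heavy-tailed settings.

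**Fitting detail.** The simulation estimated the slope with arm in the model and removed only the baseline part. Full residuals from a model containing arm would remove the difference being estimated, so the regression should omit arm. That shrinks the difference by the chance association of arm with the covariates. For three covariates unrelated to arm in 600 subjects, the expected R² is 3/599 = 0.5%, which is negligible.

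**The case against.** The SAP follows the protocol's own method. Protocol 10.1.3 is a joint list of subgroups and covariates to consider, with no commitment to adjust. Randomisation prevents systematic baseline imbalance, and the unadjusted interval already allows for chance imbalance. No precision target exists for Hb, and a move from 0.160 to 0.153 SD would be unlikely to change a conclusion. All of this stands, and it is why the point is an improvement and not a correction. It does not remove the gain: three baseline-Hb subgroups give smaller, wider comparisons, and change from baseline is described by arm only.

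A reader might infer more than the documents support:

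- *That the plan ignores baseline Hb.* It does not; the subgroup repeats and change from baseline use it.
- *That any adjustment is free.* ANCOVA replaces the Hodges–Lehmann shift with a mean difference, assumes a linear slope that titration may make unequal between arms, and can be wider with heavy tails.
- *That selective drop-out distorts this estimate.* If the lowest 15% of Hb values left one arm and the lowest 5% the other, visit means would differ by 0.274 − 0.109 = 0.165 SD with no true difference. Those rates are assumptions, and the figure concerns exploratory visit means. A subject who stops product after Week 13 still contributes to achieved Hb.
- *That the Cox and negative binomial models need baseline Hb and eGFR too.* No gain has been shown there, and added covariates turn the hazard ratio into a conditional one.

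**Conclusion.** The overall achieved-Hb estimate uses neither baseline Hb nor the randomisation factors, and a modest gain in precision is left unused. The planned analysis is valid and consistent with the protocol, so this is not an error. The size rests entirely on r: 0.5% to 13% narrower for r from 0.1 to 0.5, with the design pointing to the lower part of that range. The formula assumes a common slope. The simulation used an untruncated normal baseline and left out the randomisation factors, so it supports the direction of the result and the absence of a penalty for the rank-based form, not a precise forecast. The missing end-of-treatment difference is a separate, optional matter: by-visit Hb is exploratory, and the stated objective is to describe it within each strategy.

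**What to change.** Before unblinding, add to SAP 10.5.2 a rank-based adjusted comparison. Regress average achieved Hb on continuous baseline Hb and the two randomisation factors, without the arm term; apply the Hodges–Lehmann estimate and rank-sum interval to the residuals; report the result with the planned unadjusted estimate. This keeps the shift scale. State that the expected gain depends on r, and report the observed r.

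Optionally, add to SAP 10.5.3 a supportive repeated-measures model of Hb (arm, visit, arm by visit, baseline Hb, randomisation factors) that gives the arm difference with a 95% interval at each visit, including Week 97. State that it assumes data missing at random and estimates Hb as if subjects had stayed on product.

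The cost is SAP wording and routine programming. No new data are needed, and the planned estimate is still reported.
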